8.0 CLINICAL AND LABORATORY EVALUATIONS

Schedules shown in the Study Calendar below are provided in [Appendix I](#).

8.1 Screening/Baseline Evaluations

Baseline evaluations (including scans and x-rays) are to be conducted within 4 weeks prior to study enrollment into Segment B (Treatment Enrollment), unless otherwise specified below.

- 8.1.1 Recording of demographics, medical history, history of Centers for Disease Control and Prevention (CDC) HIV risk group and AIDS defining illnesses, physical examination (including vital signs, height, and weight), nutrition assessment, ECOG or KPS score, assessment of KS sign and symptoms, and medication review.
- 8.1.2 Diagnostic KS biopsy if not previously done at any time (can be the same biopsy collected for immunohistochemistry correlative studies). Any biopsy report is sufficient for the domestic sites; participants at the international sites require diagnosis by the AMC-approved pathologist identified for that site.
- 8.1.3 Tumor assessments with photographic record must be performed prior to initiating treatment. These may be performed on Day 0, but no earlier than 7 days before initiating study treatment. Tumor assessments and photographs should be performed as outlined in the Kaposi's Sarcoma (KS) Tumor Assessment Manual of Procedures (MOP).
- 8.1.4 Staging criteria (to be done within 4 weeks prior to study enrollment): KS staging will be based on the modified AIDS Clinical Trials Group (ACTG) Oncology Committee Staging Criteria as outlined in the KS Tumor Assessment MOP.
- 8.1.5 HIV serology if negative or not previously done.
- 8.1.6 HIV plasma viral load, and CD4 count and percentage if HIV-positive.
- 8.1.7 Chest X-ray.
- 8.1.8 Pregnancy testing by beta-HCG if female of childbearing age. Repeat pregnancy testing required immediately prior to starting standard dose nelfinavir (on Day 0) if previously performed within the 4 weeks before Day 0.
- 8.1.9 Electrocardiogram (EKG).
- 8.1.10 Complete blood count (CBC) with differential and chemistries must be performed within 4 weeks before starting treatment. Chemistries include calcium, sodium, potassium, carbon dioxide (CO₂), chloride, AST (SGOT)/ALT(SGPT), BUN, creatinine, direct and total bilirubin, fasting glucose, and triglycerides.
- 8.1.11 Optional donation to the AIDS and Cancer Specimen Resource (ACSR). (See [Appendix V](#) for ACSR Informed Consent Form and [Appendix IV](#) for ACSR Specimen Preparation and Shipping Instructions) (**for U.S. participants only**).
- 8.1.12 Correlative Studies (see [Section 2.4](#), [Appendix II](#), [Appendix IX](#), and [Appendix X](#))
 - 8.1.12.1 Oral swabs for KSHV, HSV, EBV, and CMV qPCR collected on 14 separate days pre-treatment (14 samples total) between weeks -4 and 0. Sample collection will be performed between study visits and will be self-

collected by the participant and returned at the visit to the study clinician. See [Appendix XIII](#) for participant instructions for the oral swab collection. Training and any re-training provided to the participant must be documented in the participant's study record.

- 8.1.12.2 Baseline biopsies: two biopsy specimens will be obtained prior to initiating nelfinavir: one 3 mm KS biopsy for immunohistochemistry (collected in formalin) AND one 3 mm for viral gene expression arrays (collected in RNAlater). For IHC, the same biopsy may be used for those participants that require a diagnostic KS biopsy for study entry (see [Section 8.1.2](#)). If biopsy specimens for ICH studies are deemed unusable or are inadequate to perform IHC studies, 6 additional slides from the diagnostic biopsy may be collected for analysis.
- 8.1.12.3 Blood (8.5 mL in a yellow top ACD tube) sample collected once per week during pre-treatment for a total of 2 samples for KSHV and EBV qPCR of PBMC and plasma. PBMC DNA from this sample will also be used for genotyping of CYP3A/CYP2C19 will be performed to assess nelfinavir/M8 metabolism/pharmacogenomics.

The timing of these samples is based on feasibility. For example, 2 samples can be achieved through weekly sampling in the 4 weeks pre-treatment.

- 8.1.13 Provide study drug, nutritional counseling, Participant Drug Information Handout and Wallet Card ([Appendix XIV](#)), Participant Instructions for Oral Swabs ([Appendix XIII](#)), and Participant Drug Diary (see [Appendix VII](#)). Nutritional counseling is required to ensure that participants are consuming nelfinavir with the appropriate foods. The site must query the participant regarding this information (open-ended questions are recommended) and capture the response in the source. The AMC-098 Documentation of Nutrition Assessment and Counseling source document provided on the AMC member's only website or an equivalent document may be used for this purpose.

8.2 Evaluations during Treatment

Efforts should be made to keep participants on the proper study visit schedule. Each study visit while on treatment may be conducted +/- 3 days from the evaluation schedule.

- 8.2.1 Medical history, physical exam (including vital signs and weight), medication review (adherence review), nutrition assessment, and assessment of KS sign and symptoms.
- 8.2.2 KS tumor response assessment with photographic documentation to be completed each visit, every 2 weeks as outlined in the KS Tumor Assessment MOP. Response of KS to treatment is described in [Section 9.0](#).
A chest X-ray should be performed to evaluate tumor response only for participants with pulmonary KS or new pulmonary symptoms.
- 8.2.3 Pregnancy testing by beta-HCG if female of childbearing age immediately prior to starting high-dose nelfinavir.

8.2.4 HIV plasma viral load if HIV-positive every 8 weeks while on nelfinavir.

8.2.5 Complete blood count with differential and chemistries described in [Section 8.1.10](#) every 4 weeks while on high dose nelfinavir.

8.2.6 Fasting glucose and triglycerides every 8 weeks while on high dose nelfinavir.

8.2.7 EKG 2 weeks after starting standard dose nelfinavir, and 2 weeks after starting high dose nelfinavir.

8.2.8 Correlative Studies (see [Section 2.4](#), [Appendix II](#), [Appendix IX](#), and [Appendix X](#))

8.2.8.1 Oral swabs for KSHV, HSV, EBV, and CMV, qPCR collected twice weekly for 7 weeks (14 samples) starting one week after initiation of high dose nelfinavir treatment. Sample collection between study visits will be self-collected by the participant. See [Appendix XIII](#) for participant instructions for the oral swab collection.

8.2.8.2 On-treatment biopsies

- Two weeks after initiating standard dose nelfinavir, two 3 mm KS biopsies will be obtained: one for immunohistochemistry (collected in formalin) AND one for viral gene expression arrays (collected in RNAlater).
- Two weeks after initiating high dose nelfinavir, two 3 mm KS biopsies will be obtained: one for immunohistochemistry (collected in formalin) AND one for viral gene expression arrays (collected in RNAlater).

8.2.8.3 Blood (6 mL in a lavender top EDTA tube) for assessment of nelfinavir/M8 concentrations (pharmacokinetics), prior to dosing at each study visit (every 2 weeks) while on treatment, starting on Week 1/cycle 1 through the completion of Week 15/cycle 9 (a total of 9 samples will be collected) A -3 day window is permitted.

8.2.8.4 Blood (8.5 mL in a yellow top ACD tube) sample collected at each clinic visit (every 2 weeks) while on high dose nelfinavir for KSHV and EBV qPCR of PBMC and plasma.

The timing of these samples is basing the timing on feasibility. The eight samples on treatment can be obtained twice monthly in order to coordinate the blood draw schedule with clinical/tumor assessment visits and safety lab blood draws, which will also occur on this schedule (safety labs monthly but coordinated with bi-weekly visits); this will reduce burden on participant and maximize study resources.

8.2.9 Provide study drug, nutritional counseling, Participant Instructions for Oral Swabs (one week after initiation of high dose nelfinavir, [Appendix XIII](#)), and Participant Drug Diary (see [Appendix VII](#)). Sufficient drug to provide continuous dosing between cycles/study visits should be provided as long as visits lie within the visit window.

8.3 Early Treatment Discontinuation Evaluations

8.3.1 Participants who discontinue protocol treatment for adverse events as outlined in [Section 5.0](#) should have the following evaluations and laboratory tests within 7 days after discontinuation of nelfinavir:

8.3.1.1 Medical history, physical exam (including vital signs and weight), medication review (adherence review), nutrition assessment.

8.3.1.2 KS tumor assessment with photographic documentation as outlined in the KS Tumor Assessment MOP. Response of KS to treatment is described in [Section 9.0](#).

A chest X-ray should be performed to evaluate tumor response only for participants with pulmonary KS or new pulmonary symptoms.

8.3.1.3 Complete blood count with differential, and chemistries as described in [Section 8.1.10](#).

8.3.1.4 Fasting glucose and triglycerides.

8.3.1.5 HIV plasma viral load and CD4 count if HIV-positive.

8.4 Follow-up Evaluations

8.4.1 All participants will have the following evaluations and laboratory tests 8 weeks (\pm 7 days) after discontinuation of nelfinavir. Follow-up evaluations must occur before beginning alternative therapy. If in the opinion of the treating investigator the participant needs to begin alternative therapy prior to follow up, then the follow up visit may occur earlier than 8 weeks (\pm 7 days) after discontinuation of nelfinavir.

8.4.1.1 Medical history, physical exam (including vital signs and weight).

8.4.1.2 KS tumor assessment with photographic documentation as outlined in the KS Tumor Assessment MOP. Response of KS to treatment is described in [Section 9.0](#).

A chest X-ray should be performed to evaluate tumor response only for participants with pulmonary KS or new pulmonary symptoms.

8.4.1.3 Complete blood count with differential, and chemistries as described in [Section 8.1.10](#).

8.4.1.4 Fasting glucose and triglycerides.

8.4.1.5 HIV plasma viral load and CD4 count if HIV-positive.

8.5 Final Evaluations, Off Study

At the completion of all follow-up evaluations described in [Section 8.4](#), the Off-Study Summary Form should be completed in Advantage eClinical.

8.5.1 Participants completing study per-protocol.

8.5.2 Participants who discontinue the study early.

9.0 MEASUREMENT OF EFFECT

For the purposes of this study, participants should be re-evaluated for response every 2 weeks. See [Appendix I](#) for the KS Tumor Assessment schedule.

CTEP-registered physician investigators and CTEP-registered advanced practice clinicians who are non-physician investigators (i.e., NP or PA) may perform toxicity and response assessment per local licensure requirements.

Evaluable for Toxicity: All participants will be evaluable for toxicity from the time of their first treatment with nelfinavir.

Evaluable for Objective Response: Only those participants who have measurable disease present at baseline and have received study drug will be considered evaluable for response.

Response status will be classified as complete response (**CR**), partial response (**PR**), stable disease (**SD**), or progressive disease (**PD**).

9.1 Definition of Response

Response and progression will be evaluated in this study using the AIDS Clinical Trials Groups (ACTG) response criteria for Kaposi sarcoma.

9.1.1 Complete response: Complete response (CR) is defined as the absence of any detectable residual disease, including tumor-associated edema, persisting for at least 4 weeks. In participants with pigmented (brown or tan) macular skin lesions persist after apparent complete response, biopsy of at least one representative lesion is required in order to document the absence of malignant cells. In participants known to have had visceral disease, an assessment at restaging with appropriate endoscopic or radiographic procedures should be made.

9.1.2 Partial response (PR) is defined as no new lesions (skin or oral), or new visceral sites of involvement (or the appearance or worsening of tumor-associated edema or effusions); AND

- A 50% or greater decrease in the number of all previously existing lesions lasting for at least 4 weeks; OR
- Complete flattening of at least 50% of all previously raised lesions (i.e., 50% of all previously nodular or plaque-like lesion become macules); OR
- A 50% decrease in the sum of the products of the largest perpendicular diameters of the marker lesions.

Note: Participants with residual tumor-associated edema or effusion who otherwise meet the criteria for complete response will be classified as having a partial response.

9.1.3 Stable disease is defined as any response not meeting the criteria for CR, PR, or progressive disease.

9.1.4 Progressive disease (PD) is defined as follows:

For participants with ≤ 50 cutaneous lesions

- 25% increase in the sum of perpendicular diameters of the indicator lesions, OR

- $\geq 25\%$ increase in the total lesion count, or a minimum of 5 new lesions, whichever is greater, OR
- $\geq 25\%$ increase in the number of raised lesions (minimum of 5 new raised lesions if there are very few raised lesions, for example ≤ 8), whichever is greater.

Note: There are body sites where disease is particularly difficult to evaluate, and a few new lesions may be counted in spite of the fact that a participant is not actually progressing. For example, lesions of the foot, particularly those which are flat, are difficult to evaluate because their intensity may be variable based on how much edema is present, how much the person walked the day before, how long their feet have been in a dependent position prior to the physical exam, etc.

For participants with > 50 cutaneous lesions

- $\geq 25\%$ increase in the sum of the perpendicular diameters of the indicator lesions, OR
- $\geq 25\%$ increase in the total number of lesions in the prospectively defined anatomic sites containing representative numbers of lesions, OR
- A total of 5 new lesions in anatomic sites which were previously documented as having no evidence of cutaneous disease on the whole body diagram, OR
- $\geq 25\%$ increase in the number of raised lesions (minimum of 5 raised lesions if there are very few raised lesions, for example < 8) whichever is greater. Photographic documentation of “gross” or significant progression, particularly in areas that were not being followed, will be of particular value.

In order to classify a response as PR, the participant must have at least a PR in either the cutaneous or noncutaneous sites of disease, and no evidence of progression as defined in the above criteria. In order to classify a response as a CR, the participant must have a CR in both the cutaneous (if applicable) and noncutaneous (if applicable) sites of disease, and no evidence of progression as defined by the above criteria.

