10.0 STATISTICAL CONSIDERATIONS

10.1 Study Design/Endpoints

Currently approved cytotoxic chemotherapy regimens result in a roughly 40% partial or complete response (total response) rate in persons who are not ART-naïve (who initiate ART and chemotherapy concurrently). Our hypothesis is that the dose-escalation regimen will result in at least a 20% improvement in PR or CR above the historically defined rate of spontaneous KS regression, which is 20%. We chose to evaluate a 20% improvement in total response rate because we felt that this would be both a clinically significant improvement and at least equivalent to current chemotherapy. Because NFV has many fewer toxicities and requires less monitoring, oral administration, and less cost and potential for better access compared to chemotherapy, a finding of at least equivalence could be considered an improvement over the standard-of-care. Because the cost and feasibility of using an all-oral NFV regimen in resource-limited settings would provide a significant implementation and access benefit over cytotoxic chemotherapy, we feel strongly that NFV should be proven similarly efficacious to current chemotherapy, rather than superior to it. Therefore, we have chosen a design with 90% power at a one-sided 10% significance level to test the hypothesis that 40% of participants receiving NFV at standard followed by high-dosing regimens will be able to attain PR or CR. The null hypothesis is that we will fail to detect a response superior to the rate of spontaneous tumor regression (20%). Participants from both the international and domestic protocol will contribute to the single analysis plan, which is based on HIV status and not site of recruitment.

Primary objective

To determine the efficacy of a therapeutic escalation strategy consisting of standard dose nelfinavir, followed by high dose nelfinavir, for the treatment of Kaposi sarcoma (KS) tumor lesions. The binomial proportion and its exact 95% confidence interval will be used to estimate the response rate in the study. With 36 evaluable participants, the null hypothesis will be rejected if 11 or more participants respond. Response rates will be estimated using the binomial proportion and its exact 95% confidence interval separately for HIV positive and HIV negative participants.

Secondary objectives

- To evaluate the safety of high dose nelfinavir among participants with KS.

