10.2 Sample Size/Accrual Rate

The study is designed to test the null hypothesis that the response rate is less than or equal to 20% against the alternative that it is 40% or greater with 90% power at a one-sided 10% significance level which will require a sample size of 36 evaluable participants using the exact test for a single proportion^{3,4}.

The plan is to enroll 18 participants who are HIV-positive and 18 who are HIV-negative, at an estimated accrual rate of 1-2 participants/month. Participants from both the international and domestic sites will contribute to the single analysis plan, which is based on HIV status and not site of recruitment.

Evaluable participants for all endpoints are defined as participants who meet all the eligibility criteria, enroll on the study, and receive at least one dose of treatment. Participants who enroll but are not treated will be replaced.

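### Two of the three partial-response routes in section 9.1.2 carry no 4-week persistence requirement, so a transient reading can count towards an 11-of-36 decision rule that has little slack

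*Combined protocol and SAP*

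**What the plan says.** Section 9.1.2 gives three alternative routes to PR, joined by OR:

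- Lesion count: "A 50% or greater decrease in the number of all previously existing lesions lasting for at least 4 weeks".
- Flattening: "Complete flattening of at least 50% of all previously raised lesions".
- Marker-lesion area: "A 50% decrease in the sum of the products of the largest perpendicular diameters of the marker lesions".

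Only the first has a duration. Complete response (9.1.1) must also persist for 4 weeks. Every PR further requires no new lesions, no new visceral sites, no new or worse tumor-associated edema or effusions, and no evidence of progression.

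On timing, section 9.0 says that "participants should be re-evaluated for response every 2 weeks", and section 4.1 allows up to 24 weeks of treatment. Sections 9.1.7 and 9.1.9 date response from its first documentation. Section 10.3.2 gives each participant one response category, but does not say whether this is best response, response at a fixed visit or confirmed response.

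The primary test (10.2) is to "test the null hypothesis that the response rate is less than or equal to 20% against the alternative that it is 40% or greater". It is an exact test, one-sided at 10%, planned on 36 evaluable participants to give 90% power. Section 10.1 adds: "With 36 evaluable participants, the null hypothesis will be rejected if 11 or more participants respond". It describes the 20% as a historical rate of spontaneous regression and does not say how regression was defined, how often it was assessed or whether it was confirmed.

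**The concern.** The endpoint mixes lasting and momentary responses. A participant whose lesion count halves must hold the gain for 4 weeks. One whose raised lesions flatten, or whose marker area halves, need show it only once. With repeated readings there are repeated chances for a transient or mismeasured change to meet one of the undated routes. The trial has a single arm, site clinicians assess response, and no independent response review is described.

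The primary decision compares a fixed count with a fixed 20%. If that figure describes regression that lasted, while the trial counts responses that need not last, the two are not like for like. The rate expected from an inactive drug would then exceed 20%, and the 10% error allowance could be used up by measurement alone.

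**Working it through.** **1. Reproduce the design.** Inputs from 10.1 and 10.2: N = 36, reject at 11 or more responses, null rate 0.20, alternative 0.40. With X binomial(36, p):

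- P(X ≥ 11 | p = 0.20) = 0.0889
- P(X ≥ 11 | p = 0.40) = 0.9096

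Both stated targets are met. With N = 35 and the same cut-off, power is 0.888, so 36 is needed. A cut-off of 10 gives alpha 0.168, and a cut-off of 12 gives power 0.838.

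**2. Slack in the rule.** P(X ≥ 11) if the true rate under an inactive drug is not exactly 20%:

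| True null rate | P(X ≥ 11 of 36) |
|---|---|
| 20% | 0.089 |
| 20.4% | 0.10 (crossing point) |
| 22% | 0.150 |
| 25% | 0.275 |

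**3. Number of readings.** The maximum is 24 / 2 = 12 on treatment. Sections 4.1.1 and 4.1.2 let a participant who progresses escalate at week 4 and stop after 4 weeks on high dose, which gives 8 / 2 = 4 readings.

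**4. Effect of transient readings, under stated assumptions.** Let q be the chance, per visit, that a participant who would not truly regress is read as PR. The documents give no value; 0.25% to 1% is assumed. Assume also that 20% is the rate of lasting regression and that errors are independent between visits. Then, for k readings,

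null rate = 0.20 + 0.80 × [1 − (1 − q)^k].

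Example: q = 0.5%, k = 12 gives 1 − 0.995^12 = 0.0584. The null rate is 0.20 + 0.80 × 0.0584 = 0.2467, and P(X ≥ 11) = 0.259.

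| q per visit | k = 4 | k = 6 | k = 12 |
|---|---|---|---|
| 0.25% | 0.111 | 0.123 | 0.163 |
| 0.5% | 0.136 | 0.163 | 0.259 |
| 1% | 0.193 | 0.260 | 0.486 |

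With k = 12, q of about 0.04% is enough to reach 0.10.

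**5. Correlated visits.** Errors within a participant are unlikely to be independent. In a simulation with an exchangeable latent-normal correlation of 0.8, q = 1% and k = 12, the error is 0.205 rather than 0.486.

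**6. With 4-week persistence on every route**, modelled as three consecutive 2-weekly readings, k = 12. Under independence the error is 0.0889 at q = 1% and 0.0891 at q = 2%. With correlation 0.8 and q = 1% it is 0.103.

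**7. Power if persistence lowers the true rate.** P(X ≥ 11) is 0.910 at 40%, 0.863 at 38% and 0.802 at 36%.

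**The case against.** The strongest reply is that nothing here shows inflation. The exact test holds its level at 0.089 for whatever endpoint the 20% describes. If the benchmark came from the same unconfirmed rule and a similar number of looks, there is no inflation at all. This stands: the definition behind 20% is not given, so the bias is conditional.

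A reader might infer from 9.1.2 that any one favourable reading at any of 12 visits makes a responder, and that the type I error is therefore close to one half. The documents do not support this. That any visit counts is the natural reading of 10.3.2, but it is not written there. Twelve is a maximum that early stoppers will not reach. A false PR must also pass the new-lesion, edema and progression conditions, which the formula above ignores. The figure of 0.49 combines the highest assumed q, full follow-up and independent errors.

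Nor does the protocol's remark on variable lesions ("their intensity may be variable based on how much edema is present") give evidence of false PR. It sits under progressive disease and warns about overcounting new lesions, using foot lesions, particularly flat ones, as its example. Spurious new lesions would block a PR rather than create one.

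Finally, assessment detail is delegated to the KS Tumor Assessment manual of procedures, which was not available. It may require confirmation. Section 9.1 also presents its criteria as those of the AIDS Clinical Trials Group, so changing them has some cost in comparability. Both points are fair. Neither settles whether the primary endpoint is confirmed, and the protocol should say so itself.

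**Conclusion.** The gap in the text is certain: two of three PR routes lack the persistence required of the third and of complete response, and no other part of the protocol supplies it. Its effect on the primary test is plausible in direction but not established in size. An upward bias follows if the 20% benchmark means lasting regression. A shift of about 0.4 percentage points in the null rate is then enough to take the exact error past 0.10, and a shift of 2 points takes it to 0.150.

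Beyond that, the size rests on an assumed per-visit error rate, the number of readings and the correlation between visits, none of which the documents give. The plan should be changed because the change is cheap and makes the endpoint interpretable. Inflation has not been demonstrated.

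**What to change.** - **Section 9.1.2:** apply the existing 4-week duration to all three PR routes for the primary response count, using the 2-weekly assessments already scheduled.
- **Section 10.3.2:** state that the category assigned is best confirmed response.
- **Sensitivity analysis:** report the unconfirmed response rate, under the criteria as now written, alongside the confirmed rate.
- **Late responses:** do not use the follow-up visit in 8.4.1 to overturn a late PR. It falls 8 weeks after nelfinavir stops (or earlier if alternative therapy is needed), so it tests durability off drug. List PRs first seen too late for 4-week on-treatment confirmation separately, count them only in the unconfirmed rate, and state their number.
- **Section 10.1:** state the response definition behind the 20%, so that readers can judge whether endpoint and benchmark match.

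**Cost.** No added visits. Treatment is unaffected, because stable disease and PR follow the same path at both dose levels (4.1.1, 4.1.2). The confirmed rate may be slightly lower, so the 40% alternative should be rechecked: power falls below the stated 90% if the true confirmed rate is 38% or 36% (step 7). The definition would depart slightly from the criteria as written in 9.1.2, which reporting both rates addresses.
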